#### 5.3.1.2 Units Per Month

PRBC units per month will be derived for Part A + B Baseline, Part A + B, Part B Baseline, and Part B as follows:

• Part A + B Baseline Units Per Month =

# of units in 365 days prior to first APL-2 dose\*28 365

• Part A + B Units Per Month =

# of units during Part A and Part B\*28 # of days during Part A and Part B

• Part B Baseline Units Per Month =

Apellis Pharmaceuticals, Inc.			
Protocol: APL2-CP-AIHA-208			
Part B Long Term Extension Statistical Analysis Plan	Version 1.0	08 Nov 2022	
	f units in 365 days prior to f	first 1080 mg APL–2 dose*28	
	365	365	

• Part B Units Per Month =  $\frac{\# of units during Part B*28}{\# of days during Part B}$ 

## 5.3.1.3 Transfusions Listings

The following listings will be prepared:

- Transfusion History, for all transfusions recorded in the 365 days prior to enrollment
- On-Study Transfusions, for all transfusions recorded on-study, where study part will be specified
- PRBC Transfusions and Units Per Month which will include:
  - *Part A + B PRBC*:
    - Number of Days during Part A + B Baseline Period
      (365 days) and Number of Days during Part A and B
    - Part A + B Baseline Transfusions Per Month and Part A
      + B Transfusions Per Month
    - Part A + B Baseline Units Per Month and Part A + B Units Per Month
  - **Part B PRBC**:
    - Number of Days during Part B Baseline Period (365 days) and Number of Days during Part B
    - Part B Baseline Transfusions Per Month and Part B Transfusions Per Month
    - Part B Baseline Units Per Month and Part B Units Per Month

#### 5.3.1.4 Transfusions Summary Tables

The following tabular summaries will be prepared:

- Part A + B PRBC: Summary statistics will be prepared by Cohort (Cohort 1 wAIHA / Cohort 2 CAD) for the ITT Set and Per Protocol Set who have Part A + B Baseline or at least one post-Part A + B Baseline PRBC transfusion during Part A + B phase:
  - Part A + B Baseline Transfusions Per Month
  - Part A + B Transfusions Per Month
  - Part A + B Baseline Units Per Month
  - Part A + B Units Per Month
- Part B PRBC: Summary statistics will be prepared by Cohort (Cohort 1 wAIHA / Cohort 2 CAD) for the ITT Set and Per Protocol Set who have Part B Baseline or at least one post-Part B Baseline PRBC transfusion during Part B Phase:
  - o Part B Baseline Transfusions Per Month
  - o Part B Transfusions Per Month
  - o Part B Baseline Units Per Month
  - o Part B Units Per Month

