## 5.3.1 Red Blood Cell (RBC) Transfusions

The absolute and change in number of RBC transfusions per month will be tabulated using descriptive statistics by randomized dose group, by cohort, by phase of the study (Baseline, Part A Core Study Phase and Part B Long Term Extension Phase) and over the whole on-treatment study parts (Part A and Part B combined).

Summary statistics will be presented by study phase as follows:

- Baseline:
  - Number of Transfusions and Units per month for the *n* subjects who had at least 1 infusion in the 365 days prior to first study dose
  - Number of Transfusions and Units per month for the N subjects in the dose group (i.e. all subjects in the dose group, regardless of receiving transfusions prior to enrollment)
- Post-Baseline Study Phases (Part A, Part B, Part A and B combined):
  - Number of Transfusions and Units per month for the *n* subjects who had at least 1 infusion in the respective phase
  - Number of Transfusions and Units per month for the N subjects in the dose group (i.e. all subjects in the dose group, regardless of receiving transfusions during the respective phase)
  - Change from Baseline of the Number of Transfusions and Units for the N subjects in the dose group (i.e. all subjects in the dose group, regardless of receiving transfusions during the respective phase)

Only whole blood and Packed Red Blood Cell (PRBC) transfusions will be included.

The number of RBC transfusions per month will be calculated for each part of the study as:

RBC transfusions per month

number of transfusion reported during study part \* 28 number of days in that part of study

The whole on-treatment study will be from first dose to last dose received. A similar calculation will be used for the number of units transfused per month.

The baseline number of transfusions per month will be calculated as number of transfusions reported on 12-month transfusion history /12.

All 12-month transfusion history and on study transfusion data will be listed by Cohort. A separate listing of the number of transfusions per month and number of units transfused per month for baseline, each part and over the whole on-treatment study parts will also be included.

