#### 5.3 Exploratory Efficacy and Pharmacodynamic Analyses

While the primary objective of this study is safety, exploratory efficacy and pharmacodynamic analyses will be presented. All efficacy listings will include all subjects in the Intent-to-Treat Set. All PD listings will include all subjects in the PD Set. All efficacy summaries will be evaluated on the Intent-to-Treat Set. All pharmacodynamic summaries will be evaluated on the PD Set.

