#### 5.3.1 Packed Red Blood Cell (PRBC) Transfusions

## 5.3.1.1 Transfusions Per Month

PRBC Transfusions per month will be derived for Part A + B Baseline, Part A + B, Part B Baseline, and Part B as follows:

• Part A + B Baseline Transfusions Per Month =

# of transfusions in 365 days prior to first APL-2 dose\*28 365

• Part A + B Transfusions Per Month =

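### The Part B SAP's transfusion tables leave out subjects with no baseline or on-study transfusion, so mean rates under an ITT label are inflated by N/n

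*SAP*

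**What the plan says.** The number of RBC transfusions is a listed efficacy endpoint (Part B SAP 3.2.2), with no condition that a subject must have been transfused.

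**Part B SAP (08 Nov 2022).** Section 5.3 states: "All efficacy summaries will be evaluated on the Intent-to-Treat Set". Sections 5.3.1.1 and 5.3.1.2 derive transfusions and units per 28 days for each period without restricting the subjects, and section 5.3.1.3 lists them. Section 5.3.1.4 then limits the two summary tables. The Part A + B table takes ITT and PP subjects "who have Part A + B Baseline or at least one post-Part A + B Baseline PRBC transfusion during Part A + B phase". The Part B table takes those "who have Part B Baseline or at least one post-Part B Baseline PRBC transfusion during Part B Phase". Each shows baseline and on-study rates; neither shows change from baseline. Section 4.2.2 exempts transfusions from its general change-from-baseline definitions and points to section 5.3.1, which defines none.

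**Part A SAP (27 Apr 2020), section 5.3.1.** Each on-study phase is summarised twice: for the "subjects who had at least 1 infusion in the respective phase", and for "all subjects in the dose group, regardless of receiving transfusions during the respective phase". It also plans "Change from Baseline of the Number of Transfusions and Units for the N subjects in the dose group". On products it says: "Only whole blood and Packed Red Blood Cell (PRBC) transfusions will be included". The Part B SAP names PRBC alone: "PRBC Transfusions per month will be derived for Part A + B Baseline, Part A + B, Part B Baseline, and Part B".

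**The concern.** Subjects who needed no transfusion before or during the study belong in the summary of a transfusion endpoint, with the value zero. Leaving them out under an ITT or PP title makes the cohort look more heavily transfused than it was. Any difference a reader takes between the baseline and on-study means then looks larger in absolute terms.

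The Part B table has a further gap. Its baseline is the year before the first 1080 mg dose, most or all of which is time already on APL-2. A subject who stayed transfusion-free through that year and through Part B is not in the table. Reduced transfusion dependency is a benefit the protocol hopes to see (7.3 and 12.7.1), so the table omits the subjects who best show it being sustained.

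The study is purely descriptive (Part B SAP 4.3). These tables are therefore the reported result for the endpoint, with no model or test behind them to correct the denominator.

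**Working it through.** **Inputs**

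- Table membership: Part B SAP 5.3.1.4.
- Subject rates: count × 28 / 365 at baseline and count × 28 / days in the part on study (Part B SAP 5.3.1.1); units likewise (5.3.1.2).
- Cohort size: target 12 (Part B SAP 3.3).
- Numbers who rolled over and who were transfused: not given. N and n below are assumptions.
- The plan states no figure on this point, so there is none to reproduce.

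**Step 1: the reading.** Having a baseline could mean only having a baseline value. But the baseline rate is a count over 365 days, and a subject with no transfusions has the value 0. Every subject with a history would then qualify and the second half of the condition would do nothing. The restriction has effect only if it means a baseline transfusion or an on-study one.

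**Step 2: the factor.** Let N be the subjects in the analysis set and n those in the table. Each of the N − n excluded subjects has rate 0 in both periods. The sum S of subject rates is therefore the same with or without them:

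- table mean = S / n
- all-subject mean = S / N
- table mean / all-subject mean = N / n

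The same holds for baseline rate, on-study rate and their difference. In on-study mean / baseline mean, the factor cancels.

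**Step 3: the range, assuming N = 12 in a cohort**

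| n in table | N/n |
|---|---|
| 12 | 1.00 |
| 9 | 1.33 |
| 6 | 2.00 |
| 4 | 3.00 |
| 3 | 4.00 |

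**Step 4: an assumed data set.** Take 12 subjects. Subjects 1 to 4 have 6, 4, 2 and 1 transfusions in the baseline year. Over 336 days on study, subjects 1, 2 and 5 have 2, 1 and 1. All other counts are zero, so n = 5.

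- Baseline sum: 13 × 28 / 365 = 0.997. On-study sum: 4 × 28 / 336 = 0.333.
- Part B SAP rule (÷ 5): 0.199 and 0.067, difference −0.133.
- All subjects (÷ 12): 0.083 and 0.028, difference −0.055.
- Factor: 12 / 5 = 2.4 for all three. Ratio of means: about 0.33 either way.
- Part A SAP transfused-only rule, on the same 28-day basis: 0.997 / 4 = 0.249 at baseline and 0.333 / 3 = 0.111 on study. The two means come from different sets of subjects.

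The Part B subset therefore matches neither Part A denominator.

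**Step 5: the Part B window.** For a first 1080 mg dose on Day 336, the preceding 365 days are Days 1 to 335 (335 days on treatment) plus 30 days before the first dose. A subject transfused only earlier in the pre-study year, and never again, is in the Part A + B table but not in the Part B table. The two tables can rest on different subjects of one cohort under the same label.

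**Step 6: the baseline formula.** The Part A SAP divides the 12-month count by 12; the Part B SAP multiplies it by 28/365. The ratio is (1/12) / (28/365) = 1.086, so the same history gives a baseline 8.6% higher under the Part A SAP.

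**The case against.** **Nothing is lost.** Rates are derived without restriction, and section 5.3 puts all ITT subjects in the efficacy listings. A reader might infer that the Part B SAP computes rates only in transfused subjects; it does not. With N and n shown, the all-subject mean is the table mean × n/N. This stands and keeps the matter to two summary tables. It does not justify leaving readers to rebuild a listed endpoint.

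**The wording is loose.** Read with section 5.3, section 5.3.1.4 might have been meant to cover everyone. Then the text still needs correcting, because a programmer following it would filter.

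**The effect is not exaggerated in relative terms.** This is right. A reader might infer that the restriction overstates the treatment benefit in general. The ratio of means is unchanged, and a subject admitted only by an on-study transfusion counts against benefit. Only levels and absolute differences grow, and the plan tabulates no difference; a reader would have to subtract.

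**Part A also has transfused-only rows.** It does, and its baseline and on-study subsets can differ, which is weaker than the Part B rule of keeping the same people in both periods. But Part A sets all-subject rows beside them.

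**Other tables may fill the gap.** The baseline characteristics table (Part B SAP 5.1.3) includes baseline transfusions per month without the restriction. It covers baseline only, and its formula is printed with 365/28 where section 5.3.1.1 has 28/365, a factor of (365/28)² ≈ 170. The list of planned outputs (Appendix 8.2) is not in the text available here, so an all-subject table named only there cannot be ruled out.

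**Whole blood may never have been given.** Nothing in the documents says it was. The product difference is an inconsistency of definition with no known numerical effect.

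**Conclusion.** The point holds for the summary tables in Part B SAP 5.3.1.4. They contradict section 5.3 of the same SAP and omit the all-subject rates and change from baseline that the Part A SAP provides. Followed as written, they show mean rates N/n times the all-subject means under an ITT or PP title. The Part B table also omits subjects who were transfusion-free in the 365 days before the first 1080 mg dose and throughout Part B.

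The factor N/n is exact; its value here is unknown. It is 1.0 if every subject was transfused in one period or the other, and 1.33 to 4.0 for n from 9 down to 3 under the assumed N = 12. None of these is an estimate for this trial.

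A reader might also infer that all-subject rows would make Part B directly comparable with Part A. They would not. The Part B ITT Set holds only rollover subjects given at least one 1080 mg dose (Part B SAP 4.1), and its tables are by cohort rather than by dose group within cohort.

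This is a correction to the reporting of an exploratory efficacy endpoint in a small pilot study. It is worth making because it is nearly free, and it affects no test or decision rule.

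**What to change.** In Part B SAP 5.3.1.4:

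- Base the main Part A + B and Part B tables on all ITT subjects, and repeat them for all PP subjects, counting zeros. Show baseline, on-study and change from baseline for transfusions and units per 28 days, with N printed.
- Keep the transfused-only rows as a supplementary block, labelled with the rule for entry and with n.
- Define the transfusion change from baseline in section 5.3.1, since section 4.2.2 refers the reader there.

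Across both SAPs, use one product definition (whole blood plus PRBC) and one baseline formula (count × 28/365 rather than count/12). The Part B SAP says that the Part A interim analysis was produced under the Part A SAP. Any Part A rates placed beside the new tables should therefore be recomputed on this basis or footnoted.

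State in the report that comparison with Part A remains limited, because the Part B ITT Set contains only rollover subjects dosed at 1080 mg.

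The cost is a few lines of SAP text and some table rows. Subject-level rates are already derived and listed, so no new data are needed.

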# 5.3.2 Functional Assessment of Chronic Illness Therapy (FACIT) Fatigue Scale

### 5.3.2.1 FACIT Fatigue Score

The FACIT Fatigue Scale (Version 4) questionnaire is an exploratory efficacy endpoint. The FACIT Fatigue Scale is a 13 item Likert scaled instrument which is self-administered by the subjects during clinic visits. Subject are presented with 13 statements and asked to indicate their responses as it applies to the past 7 days. The 5 possible responses are 'Not at all' (0), 'A little bit' (1), 'Somewhat' (2), 'Quite a bit' (3)

and 'Very much' (4). With 13 statements, the total score has a range of 0 to 52. Before calculating the total score, most responses (all except Item Codes 5 and 7 of the FACIT Fatigue Scale Version 4) are reversed to ensure that the higher score corresponds to a higher quality of life.

Study Day 1 will be considered the Part A+ B Baseline for the FACIT assessment. If this is missing, change from Part A + B baseline will not be calculated. Part B Baseline will be considered as the last assessment before the first 1080mg APL-2 dose for each subject.

The FACIT and all related works are owned and copyrighted by, and the intellectual property of PPD, Ph.D. Permission for use of the FACIT-FATIGUE questionnaire is obtained by contacting PPD at [contact].

## 5.3.2.2 FACIT Listings

The following listings will be prepared:

- FACIT Fatigue Scale Questionnaire Responses
- FACIT Fatigue Score and Change from Baseline which will include:
  - $\circ \quad \underline{Part A + B}:$ 
    - FACIT Fatigue Score Results at all Part A + B visits with Change from Part A + B Baseline and Percent Change from Part A + B Baseline

## • Part B:

 FACIT Fatigue Score Results at all Part B visits with Change from Part B Baseline and Percent Change from Part B Baseline

#### 5.3.2.3 FACIT Summary Tables

The following tabular summaries will be prepared by Cohort (Cohort 1 wAIHA / Cohort 2 CAD) for ITT Set and Per Protocol Set for the following:

### • Part A + B FACIT Fatigue Score::

- FACIT Fatigue Score results at all scheduled visits through Part
  A Visit 15 and from Part B Baseline through the end of study
- Change from Part A + B Baseline FACIT Fatigue Score at all post-baseline visits through Part A Visit 15 and from Part B Baseline through end of study
- Percent Change from Part A + B Baseline FACIT Fatigue
  Score at all post-baseline visits through Part A Visit 15 and
  from Part B Baseline through end of study

## • Part B FACIT Fatigue Score:

- FACIT Fatigue Score results at Part B Baseline and all scheduled Part B visits
- Change from Part B Baseline FACIT Fatigue Score ay all postbaseline visits
- Percent Change from Part B Baseline FACIT Fatigue Score at all post-baseline visits

### 5.3.2.4 FACIT Summary Figures

The following figures will be prepared:

- Part A + B FACIT Fatigue Score: Mean score ± SE will be presented by Cohort (Cohort 1 wAIHA / Cohort 2 CAD) for the ITT Set and Per Protocol Set for the following:
  - FACIT Fatigue Score results at all scheduled visits through Part
    A Visit 15 and from Part B Baseline through end of study

 Change from Part A + B Baseline FACIT Fatigue Score at all post-baseline visits through Part A Visit 15 and from Part B Baseline through end of study

Version 1.0

### • Part B FACIT Fatigue Score:

 Change from Part B Baseline FACIT Fatigue Score from Part B Baseline through end of study

### 5.3.3 Linear Analog Self-Assessment (LASA)

### 5.3.3.1 LASA Overall Quality of Life and Subscales

The LASA, which consists of five single statements asking respondents to rate, on zero to ten scales, their perceived level of functioning (see Protocol Section 17.2).

Specific domains include physical well-being (i.e., fatigue, activity level), emotional well-being (i.e., depression, anxiety, stress), spiritual well-being (i.e., sense of meaning), and intellectual well-being (i.e., ability to think clearly, concentrate). An item for overall quality of life (QoL) is also included. The Likert scales run from 0 (as bad as it can be) to 10 (as good as it can be), where higher ratings suggest higher QoL.

Study Day 1 will be considered the Part A+ B Baseline for the LASA assessment. If this is missing, change from Part A + B baseline will not be calculated. Part B Baseline will be considered as the last assessment before the first 1080mg APL-2 dose for each subject.

### 5.3.3.2 LASA Listings

The following listings will be prepared:

 LASA Domain Responses (Physical Well Being, Emotional Well Being, Spiritual Well Being, Intellectual Well Being, and Overall Quality of Life) and Change from Baseline which will include:

#### ○ Part A + B:

- LASA Domain Results at all Part A + B visits with Change from Part A + B Baseline and Percent Change from Part A + B Baseline
- Part B:
  - LASA Domain Results at all Part B visits with Change from Part B Baseline and Percent Change from Part B Baseline

#### 5.3.3.3 LASA Domain Summary Tables

The following tabular summaries will be presented for each of the LASA Domains (Overall Quality of Life, Physical Well Bring, Emotional Well Being, Spiritual Well Being, and Intellectual Well Being) by Cohort (Cohort 1 wAIHA / Cohort 2 CAD) for the ITT Set and Per Protocol Set for the following:

- Part A + B LASA Domain Scores:
  - LASA Domain Score results at all scheduled visits through Part
    A Visit 15 and from Part B Baseline through end of study
  - Change from Part A + B Baseline LASA Domain Score at all post-baseline visits through Part A Visit 15 and from Part B Baseline through end of study
  - Percent Change from Part A + B Baseline LASA Domain
    Score at all post-baseline visits through Part A Visit 15 and
    from Part B Baseline through end of study
- Part B LASA Domain Scores:
  - LASA Domain Score results at Part B Baseline and all scheduled Part B visits

- Change from Part B Baseline LASA Domain Score at all postbaseline visits
- Percent Change from Part B Baseline LASA Domain Score at all post-baseline visits

### 5.3.3.4 LASA Domain Summary Figures

The Mean score ± SE figures will be presented for each of the LASA Domains (Overall Quality of Life, Physical Well Bring, Emotional Well Being, Spiritual Well Being, and Intellectual Well Being) by Cohort (Cohort 1 wAIHA / Cohort 2 CAD) for the ITT Set and Per Protocol Set for the following:

- Part A + B LASA Domain Scores:
  - LASA Domain Score results at all scheduled visits through Part
    A Visit 15 and from Part B Baseline through end of study
  - Change from Part A + B Baseline LASA Domain Score at all post-baseline visits through Part A Visit 15 and from Part B Baseline through end of study
- Part B LASA Domain Scores:
  - Change from Part B Baseline LASA Domain Score from Part B Baseline through end of study

### 5.3.4 Efficacy Laboratory Parameters

### 5.3.4.1 Parameters and Normalization

Efficacy laboratory parameters include the following:

- 1. Lactate Dehydrogenase
- 2. Reticulocytes
- 3. Hemoglobin
- 4. Haptoglobin
- 5. Indirect Bilirubin

Study Day 1 will be considered the Part A+ B Baseline for the efficacy lab assessments. If this is missing, the screening assessment, if available, will be used as Part A + B Baseline. Part B Baseline will be considered as the last assessment before the first 1080 mg APL-2 dose for each subject.

Some laboratory parameters will be collected by central and local laboratories. In the cases where a visit's sample is collected on both central and local labs, the central lab result will be presented in the TLF. In the cases where only local labs are available, the local lab data will be normalized using the procedure outlined in Section 5.2.2.1.

### 5.3.4.2 Efficacy Laboratory Listings

The following listings will be prepared:

• Efficacy Laboratory Results and Change From Baseline will be presented in separate listings which will include:

### $\circ \quad \underline{Part A + B}:$

Lab Results at all Part A + B visits with Change from
 Part A + B Baseline and Percent Change from Part A +
 B Baseline

## • Part B:

 Lab Results at all Part B visits with Change from Part B Baseline and Percent Change from Part B Baseline

### 5.3.4.3 Efficacy Laboratory Summary Tables

The following tabular summaries will be presented for each efficacy laboratory parameter by Cohort (Cohort 1 wAIHA / Cohort 2 CAD) for the ITT Set and Per Protocol Set for the following:

### Part A + B Lab Results:

- Lab results at all scheduled visits through Part A Visit 15 and from Part B Baseline through end of study
- Change from Part A + B Baseline lab result at all post-baseline visits through Part A Visit 15 and from Part B Baseline through end of study
- Percent Change from Part A + B Baseline lab result at all postbaseline visits through Part A Visit 15 and from Part B Baseline through end of study

## • Part B Lab Results:

- Lab results at Part B Baseline and all scheduled Part B visits
- Change from Part B Baseline lab result at all post-baseline visits
- Percent Change from Part B Baseline lab result at all postbaseline visits

